14.3 Slit-Lamp Biomicroscopy Examination

Slit-lamp biomicroscopy examinations will be conducted on both eyes at all scheduled visits, Pre- and Post-CAE®. The slit lamp findings will include examinations of the cornea, conjunctiva, anterior chamber, iris, lens and lid. Each parameter will be graded as normal or abnormal. Abnormal findings will be further classified as not clinically significant (NCS) or clinically significant (CS).

Slit lamp findings will be summarized by treatment group and visit, for the worst eye and fellow eye separately, using qualitative summary statistics (frequency counts and percentages). Percentages will be based on the number of subjects with non-missing values for the treatment group at a given visit.

A shift table will show changes from baseline (Visit 2b (Day 1), Pre-CAE®) to all observations at later study visits and time points. The data for slit lamp biomicroscopy will be presented in a listing.

14.4 Corneal Sensitivity (Cochet-Bonnet)

Corneal Sensitivity will be performed at Visits 1b (Day -7 ± 1) Pre CAE® and 4b (Day 29 ± 2) Pre CAE®. Corneal sensitivity will be summarized for both eyes combined by visit and treatment group using quantitative summary statistics. Results will be listed for both eyes at each visit.

14.5 Undilated Fundoscopy

Undilated fundoscopy examinations will be conducted on both eyes at Visit 1b (Day -7 ± 1) Post-CAE® and Visit 4b (Day 29 ± 2) Post-CAE®. The fundus pathology findings will include examinations of the vitreous, retina, macula, choroid, and optic nerve, and be recorded as normal, abnormal (NCS), or abnormal (CS). Summaries of undilated fundoscopy findings will be presented by treatment and visit, for the worst eye and fellow eye separately, using frequency counts and percentages. Percentages will be based on the number of subjects with non-missing values for the treatment group at a given visit.

A shift table will show changes from baseline (Visit 1b (Day -7 ± 1), Post-CAE® to Visit 4b (Day 29 ± 2), Post-CAE®) on the above variables. The data for undilated fundoscopy will be presented in a listing.

14.6 Intraocular Pressure (IOP)

IOP will be measured at Visits 1b (post-CAE®) and 4b (post-CAE®). IOP will be summarized for both eyes combined by visit and treatment group using quantitative summary statistics. At Visit 4b, an IOP of ≥ 21 mmHg AND ≥ 10 mmHg over baseline (Visit 1b) will be considered an AE, and presented in the tabular summary. Results will be listed for both eyes at each visit.

15. Tolerability Analyses

Two tools will be used to assess drop comfort, each of which will be assessed at Visit 2b (Day 1) and Visit 3b (Day 15 ± 1), following the first dose of study drug.

subject will be used for this analysis. Drop comfort will be summarized using quantitative summary statistics. Statistical comparisons will employ two-sample *t*-tests as the primary method of analysis.

- Ora Calibra® Drop Comfort Questionnaire will be used to assess drop comfort

Drop Comfort Questionnaire responses will be summarized using qualitative summary statistics. Subjects with at least one negative response will also be summarized.

16. Exploratory Efficacy Analyses

The continuous and ordinal secondary efficacy variables collected at each visit will be summarized descriptively (n, mean, SD, median, minimum and maximum), and analyzed with two-sample *t*-tests comparing the active treatment groups to placebo. All visit-based data will be analyzed at each visit as well as change from baseline. A Wilcoxon rank sum test and an ANCOVA model adjusting for baseline will also be assessed where appropriate. Corneal fluorescein staining by region and total (Ora and NEI scales), lissamine green staining by region, TFBUT, conjunctival redness, unanesthetized Schirmer's test, ocular symptoms (Ora Calibra® scales and VAS), OSDI®, ocular discomfort and changes from baseline in these measures will be analyzed by visit and time point, where applicable (i.e., pre- and post-

[figure not shown]
CAE[®]), using two-sample *t*-tests and Wilcoxon rank sum tests. Changes from baseline will also be analyzed using ANCOVA models adjusting for baseline values. For the measures of symptoms during CAE[®], the ANCOVA models will also include the pre-CAE[®] measure as a covariate. Symptoms recorded on the daily diary will be analyzed using repeated measure ANCOVA models, where baseline scores are calculated as the average scores in the run-in period and post-baseline scores are calculated as weekly morning, afternoon, evening, and daily averages.

The efficacy analyses will be performed using observed data. In addition, for key endpoints of corneal fluorescein staining using the Ora Calibra scale and ocular discomfort, missing data will be imputed using LOCF and multiple imputation methods to assess robustness of the results. The PP population with observed data will also be analyzed as an additional sensitivity analysis.

Adjustments for multiplicity will not be employed in this exploratory Phase 2 study.

[figure not shown]

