#### **Post- CAE® Procedures**

- Ora Calibra® Ocular Discomfort
- Ora Calibra® Ocular Discomfort & 4-Symptom questionnaire
- Slit-lamp biomicroscopy
- Ora Calibra® Conjunctival Redness
- TFBUT
- Fluorescein staining – Ora Calibra® and NEI scale
- Lissamine Green staining – Ora Calibra® and NEI scale
- Adverse Event Query
- Review of qualification criteria
- Randomization & Dispensation of study drug kit according to randomization for TID dosing until Visit 3b
- Subject self-administers first dose of study drug, OU
- Ora Calibra® Drop Comfort and Questionnaire
- Wait at least 15 minutes from in office dose to Impression Cytology
- Impression cytology (OPIA Eyeprim™) – to be performed on the “worst eye” as defined in Section 10.4.2. Anesthetic may be used at the discretion of the Investigator
- Subjects will be instructed to dose in each eye three times daily (morning, afternoon, and in the evening before bed)
- Dispensation of diaries:
  - Subjects will be instructed to complete diary symptoms TID prior to drop instillation in the morning, afternoon, and in the evening before bed until Visit 3b;
  - Subjects will be instructed to complete their diary TID to account for each dose of study drug taken;

- Subjects will be instructed to complete their diary and dose in each eye in the afternoon and before bed on the evening of Visit 2b;
- Subjects will be instructed to complete their diary on the morning of their next visit (Visit 3b);
- Subjects will be instructed to not dose with study drug on the morning of their next visit (Visit 3b);
- Subject will remain at the site for at least 30 minutes after instillation of study drug
- Qualified subjects will be scheduled for Visit 3b.

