#### 10.4.7 Exploratory Efficacy Analyses

The continuous and ordinal secondary efficacy variables collected at each visit will be summarized descriptively (n, mean, standard deviation, median, minimum and maximum), and analyzed with two-sample t-tests comparing the active treatment groups to placebo. All visit-based data will be analyzed at each visit as well as change from baseline. A Wilcoxon rank sum test and an ANCOVA model adjusting for baseline will also be assessed where appropriate. Corneal fluorescein staining by region and total (Ora and NEI scales), lissamine green staining by region, tear film break-up time, conjunctival redness, unanesthetized Schirmer's test, ocular symptoms (Ora Calibra® scales and VAS), OSDI®, ocular discomfort and changes from baseline in these measures will be analyzed by visit and time point, where applicable (i.e., pre- and post-CAE®), using two-sample t-tests and Wilcoxon rank sum tests. Changes from baseline will also be analyzed using ANCOVA models adjusting for baseline values. For the measures of symptoms during CAE®, the ANCOVA models will also include the pre-CAE® measure as a covariate. Drop comfort will be summarized descriptively. Symptoms recorded on the daily diary will be analyzed using repeated measure ANCOVA models, where baseline scores are calculated as the average scores in the run-in period and post-baseline scores are calculated as weekly morning, afternoon, evening, and daily averages.

A full statistical analysis plan (SAP) will be finalized before database lock and unmasking.

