mmHg	Millimeters of Mercury
OD	Right Eye
OPI	Ocular Protection Index
OS	Left Eye
OSDI [®]	Ocular Surface Disease Index
OU	Both Eyes
OTC	Over-the-counter
PMNs	Polymorphonuclear Leucocytes
PP	Per Protocol
PT	Preferred Term
TID	Three Times a Day
SAE	Serious Adverse Event
SAP	Statistical Analysis Plan
SDC	Statistics and Data Corporation
SOC	System Organ Class
SOP	Standard Operating Procedure
TFBUT/TBUT	Tear Film Break-up Time
TEAE	Treatment Emergent Adverse Event
VA	Visual Acuity
VAS	Visual Analogue Scale
WHO	World Health Organization

1. Introduction

The purpose of this statistical analysis plan (SAP) is to describe the planned analyses and reporting for protocol TOP1630-TV-04, version 2.0 dated 20Jan2017.

This SAP is being written with due consideration of the recommendations outlined in the most recent International Conference on Harmonization (ICH) E9 Guideline entitled Guidance for Industry: Statistical Principles for Clinical Trials and the most recent ICH E3 Guideline, entitled Guidance for Industry: Structure and Content of Clinical Study Reports (CSR).

This SAP describes the data that will be analyzed and the subject characteristics, efficacy, and safety assessments that will be evaluated. This SAP provides details of the specific statistical methods that will be used. The statistical analysis methods presented in this document will supersede the statistical analysis methods described in the clinical protocol. If additional analyses are required to supplement the planned analyses described in this SAP they may be completed and will be identified in the CSR.

2. Study Objectives

The primary objective of this study is to compare the safety and tolerability of TOP1630 Ophthalmic Solution to placebo. The secondary objectives are to compare the efficacy of TOP1630 Ophthalmic Solution to placebo for the treatment of the signs and symptoms of dry eye syndrome.

3. Study Variables

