5.1 Method of Assigning Subjects to Treatment Groups

Prior to initiation of study run-in (at Visit 1b), each subject who qualifies for entry will be assigned a screening number. All screening numbers will be assigned in strict numerical sequence at a site and no numbers will be skipped or omitted. If all inclusion and exclusion criteria are met at Visits 1b and 2b, each qualifying subject will then be assigned a randomization number at the end of Visit 2b.

Subjects who meets all qualification criteria will be randomly assigned to masked treatment using a 1:1 (approximately 30 subjects in the TOP1630 arm and approximately 30 in the placebo arm) assignment ratio. Subjects will be randomized by assignment of the next 4-digit randomization number available (3001-3100). No randomization numbers will be skipped or omitted. An independent randomization specialist who is not otherwise involved in the trial will generate the randomization code utilized at site. The unique randomization list will assign masked study kit numbers to be dispensed to each enrolled subject. At the end of Visit 1b, qualified subjects will receive a kit of run-in (Placebo) for one week, dosing TID until Visit 2b. At the end of Visit 2b and 3b, subjects will be given two kits of 24 bottles each of TOP1630 Ophthalmic Solution or placebo for TID dosing. At Visits 3b and 4b, remaining/unused study drug will be collected from subjects for drug accountability.

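### SAP 15 compares drop comfort by a valid but unadjusted t-test; adding the pre-randomisation Visit 2b ocular discomfort score as a covariate may narrow the interval at almost no cost

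*SAP*

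**What the plan says.** Both documents make safety and tolerability the primary objective: "The primary objective of this study is to compare the safety and tolerability of TOP1630 Ophthalmic Solution to placebo". SAP Section 15 covers tolerability through two drop comfort tools, "each of which will be assessed at Visit 2b (Day 1) and Visit 3b (Day 15 ± 1), following the first dose of study drug". For the score it states: "Drop comfort will be summarized using quantitative summary statistics. Statistical comparisons will employ two-sample *t*-tests as the primary method of analysis". The visible text of that section mentions no covariate, ANCOVA or rank test. The text just before this sentence is missing from the public copy, so the scale and part of the eye derivation cannot be seen.

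Elsewhere the SAP does adjust. Section 16 says of the efficacy measures: "Changes from baseline will also be analyzed using ANCOVA models adjusting for baseline values". For symptoms during the CAE it adds the pre-CAE measure as a further covariate.

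Protocol Section 8.3.1 gives the order of events at Visit 2b. The post-CAE list opens with the Ora Calibra Ocular Discomfort rating, followed by the "Ora Calibra® Ocular Discomfort & 4-Symptom questionnaire". Slit lamp, redness, TFBUT and the two stains come next, then the adverse event query and eligibility review, then randomisation. After that: "Subject self-administers first dose of study drug, OU". Drop comfort follows the dose. SAP Section 5.1 confirms the timing: "each qualifying subject will then be assigned a randomization number at the end of Visit 2b".

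The status of the comparison is unsettled. Protocol Section 10.4.7 says: "Drop comfort will be summarized descriptively", and Protocol Section 10.4.6 also describes summaries only. SAP Section 3.1 lists drop comfort as a safety variable, SAP Section 14 rules out inferential testing of safety variables, and SAP Section 18 declares no change from the protocol's analyses.

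**The concern.** Drop comfort has no baseline of its own, which may be why Section 15 has no adjusted analysis. But the Visit 2b drop goes into eyes that have just been through a 90-minute CAE, and how uncomfortable the eyes already are may influence how the drop is rated. If so, the t-test leaves that between-subject variation in its error term, although a rating that could explain part of it is already on the database and cannot have been affected by treatment.

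At stake is the width of one interval on a measure that serves the primary objective. With about 30 subjects per arm, a wide interval makes it hard to tell a drop as comfortable as vehicle from a comparison too imprecise to show a difference.

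**Working it through.** **The plan's own figure.** The only probability stated (SAP Section 6, Protocol Section 10.3) is 79% for detecting adverse events with a rate of 5%. It reproduces per arm: 1 − 0.95^30 = 0.785. It does not bear on drop comfort, for which the documents give no SD, target difference or power. Results below are therefore in SD units.

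**Inputs from the documents**
- 30 subjects per arm, N = 60 (SAP 4.1).
- Two-sided 90% intervals (SAP 9.4).
- Covariate: Visit 2b post-CAE Ocular Discomfort, rated before randomisation (Protocol 8.3.1, SAP 5.1). It should be available for essentially every randomised subject, because the worst-eye tie-break in SAP 9.1 already uses it.

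**Assumption.** r, the correlation between that score and drop comfort, is not in the documents. A range is shown.

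**Unadjusted comparison.** Half-width = t(0.95, 58) × √(2/30) = 0.432 SD.

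**Adjusted comparison.** The variance of the ANCOVA difference relative to the t-test is (1 − r²) × (1 + 1/(N − 4)) = (1 − r²) × (57/56). The second factor is the price of estimating the slope with chance imbalance in the covariate. The half-width is t(0.95, 57) × √(2/30) × √(variance ratio). The equivalent total N is 60 divided by the variance ratio.

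| Assumed r | Variance ratio | 90% half-width (SD) | Change in width | Equivalent N |
|---|---|---|---|---|
| 0 | 1.018 | 0.436 | about 1% wider | 59 |
| 0.2 | 0.977 | 0.427 | about 1% narrower | 61 |
| 0.3 | 0.926 | 0.415 | about 4% narrower | 65 |
| 0.5 | 0.763 | 0.377 | about 13% narrower | 79 |
| 0.6 | 0.651 | 0.348 | about 19% narrower | 92 |

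Break-even is where (1 − r²) × (57/56) = 1, so r² = 1/57 and r is about 0.13. A simulation of 20,000 trials gave variance ratios of 1.02, 0.93 and 0.76 at r = 0, 0.3 and 0.5, in line with the formula.

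**Visits.** The table applies to each visit with its own r. For Visit 3b the Day 1 score would predict a rating two weeks later after a different CAE, so r may be lower there. The discomfort score taken at Visit 3b itself is post-randomisation and may be changed by treatment, so it is not a suitable covariate.

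**The case against.** The strongest case against is that nothing here is wrong. A t-test on randomised arms is valid, the study is exploratory and not powered for efficacy, and the documents attach no margin or decision rule to the drop comfort comparison. That stands.

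The gain may also be small. The two ratings measure different things: dry-eye discomfort and the feel of a drop. Inclusion criterion 12b admits only subjects who reach discomfort of at least 3 at two or more consecutive CAE time points (4 if they start at 3), at both Visits 1b and 2b. This may compress the covariate's range and lower r. The rating also comes first after the CAE, before the post-CAE dye tests, so it does not record the eye's state at instillation. These points stand. They are reasons to expect the lower rows of r, not reasons why adjustment would be invalid.

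A reader might infer that precision is certainly being thrown away, or that pre-drop discomfort must determine drop comfort. The documents support neither, since they give no correlation and the benefit disappears below about r = 0.13.

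Finally, it can be said that whether Section 15 should contain any test comes first. That also stands, and the fix has to deal with it.

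**Conclusion.** The point holds as an efficiency improvement. SAP Section 15 plans an unadjusted comparison although a true pre-randomisation covariate is already collected. The size is conditional on an assumed r: from about a 1% loss in interval width at r = 0 to 13% narrower at r = 0.5 and 19% at r = 0.6. The gain at Visit 3b may be smaller than at Visit 2b.

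The balance favours adding the analysis because the worst case costs about one degree of freedom, and because the SAP already reports ANCOVA beside t-tests for its efficacy endpoints. It does not follow that the t-test is wrong or must be dropped, or that the tolerability objective is compromised: drop comfort is one measure among several under that objective. The conclusion covers visible text only; a covariate named in the missing lines would change it.

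**What to change.** Before unmasking, add to SAP Section 15 an ANCOVA of the drop comfort score, fitted separately at Visits 2b and 3b, with treatment and the Visit 2b post-CAE Ora Calibra Ocular Discomfort score as terms. Derive the covariate over the same eye or eyes as the comfort score. Use the Visit 2b value at both visits. Report the adjusted difference with its 90% CI beside the existing analysis.

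In the same edit, settle whether drop comfort is to be tested. SAP 15 must be reconciled with SAP 3.1 and 14 and with Protocol 10.4.6 and 10.4.7. One way is to give the differences and 90% CIs without p-values. Either way the plan goes beyond the protocol's descriptive summary, so record it in SAP Section 18.

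The cost is a few lines of SAP text and code. No new data, visits or subjects are needed. Timing matters: a covariate chosen after unmasking would be open to the charge of being data-driven.

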16.1 Corneal Fluorescein Staining

[figure not shown]
Corneal fluorescein staining (Ora Calibra[®] and NEI scales) will be performed pre-CAE[®] and post-CAE[®] for both eyes at Visit 1b (Day -7 ± 1), Visit 2b (Day 1, prior to treatment), Visit 3b (Day 15 ± 1) and Visit

An analysis of covariance (ANCOVA) model will also be used to compare the changes from baseline for corneal fluorescein staining in each region, as well as the corneal, conjunctival and total staining scores, as measured on the Ora Calibra[®] and NEI scales, between TOP1630 Ophthalmic Solution and Placebo.

The ANCOVA model will include terms for treatment as the main effect and baseline corneal fluorescein staining as a covariate.

16.2 Ocular Discomfort

Ocular discomfort will be assessed pre-CAE® and post-CAE® for both eyes at Visit 1b (Day -7 ± 1),

Ocular discomfort will be analyzed by visit and time point, where applicable (i.e., pre- and post-CAE® as well as the pre- to post-CAE change), using two-sample t-tests and Wilcoxon rank sum tests.

Change from baseline for ocular discomfort will be analyzed similarly to the change from baseline for corneal fluorescein staining. An ANCOVA model will be used to compare the change from baseline for ocular discomfort, as measured on the Ora Calibra® Ocular Discomfort scale, between TOP1630 Ophthalmic Solution and Placebo. The ANCOVA model will include treatment as the main effect term and baseline ocular discomfort at Day 1 (Visit 2b) as a covariate.

16.3 Lissamine Green Staining

Lissamine green staining will be graded with the Ora Calibra® and NEI scales. The Ora Calibra® Scale

16.4 Tear Film Break-Up Time

TFBUT will be measured in seconds at all scheduled visits, pre- and post-CAE®, on both eyes. For each eye, two measurements will be taken and averaged unless the two measurements are >2 seconds apart and are each <10 seconds, in which case, a third measurement would be taken and the two closest of the three will be averaged and used for analyses. If the differences between two sequential pairs of measurements are the same, e.g., 3, 6, 9 seconds, then the median of the three readings will be used for analysis. The worst eye from each subject will be used for this analysis.

TFBUT will be summarized by visit and time point (pre- and post-CAE®) for the mITT Population using quantitative summary statistics. Change from pre- to post-CAE® within each visit as well as change from baseline will also be summarized.

Statistical comparisons will employ two-sample *t*-tests as the primary method of analysis. A Wilcoxon rank sum test will also be assessed as a sensitivity analysis. Changes from baseline will also be analyzed using ANCOVA models adjusting for baseline values.

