## 5.2 Study population characteristics

### Inclusion Criteria

Subjects must meet all of the following requirements to be eligible for enrollment into the study:

For the Comfort Assessment:

1. Be at least 18 years of age;
2. Provide written informed consent;
3. Have a patient reported history of dry eye for at least 6 months prior to Visit 1a;
4. Have a history of use or desire to use eye drops for dry eye symptoms for at least 6 months prior to Visit 1a;

For the Safety and Efficacy Assessment:

All of the above criteria (at Visit 1b), and:

5. Report a score of  $\geq 2$  in at least one symptom of the Ora Calibra® Ocular Discomfort & 4-Symptom Questionnaire at Visits 1b and 2b;
6. Report an OSDI® score  $\geq 18$  at Visits 1b and 2b;
7. Have a conjunctival redness score of  $\geq 1$  according to the Ora Calibra® scale in at least one eye at Visits 1b and 2b;
8. Have a tear film break-up time (TFBUT)  $>1$  and  $< 7$  seconds in at least one eye at Visit 1b and 2b;
9. Have a Schirmer's Test score of  $\leq 10$  mm and  $\geq 1$  mm in at least one eye at Visits 1b and 2b;
10. Have a corneal fluorescein staining score of  $\geq 2$  according to the Ora Calibra® scale in at least one region (e.g. inferior, superior, or central) in at least one eye at Visits 1b and 2b;
11. Have a total lissamine green conjunctival score of  $\geq 2$ , based on the sum of the temporal and nasal regions of the conjunctiva according to the Ora Calibra® scale in at least one eye at Visits 1b and 2b;
12. Demonstrate a response to the CAE® at Visits 1b and 2b as defined by:
  - a. Having at least a  $\geq 1$  point increase in fluorescein staining in the inferior region in at least one eye following CAE® exposure on the Ora Calibra® scale; and
  - b. Reporting an Ocular Discomfort score  $\geq 3$  at 2 or more consecutive time points in at least one eye during CAE® exposure on the Ora Calibra® scale (if a subject has an Ocular Discomfort rating of 3 at time = 0 for an eye, s/he must report an Ocular Discomfort rating of 4 for two consecutive measurements for that eye).

13. Have at least one eye (the same eye) satisfy all criteria for 7, 8, 9, 10, 11, and 12 above;
14. At Visit 2b, subjects must have at least 5 days' worth of diary symptom data and deemed by the PI to be 80% compliant with vehicle eye drops.

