3.4 Statistical Hypotheses

The null and alternative hypotheses, based on the exploratory efficacy variables, are as follows:

H_0 : There is no difference between the TOP1630 Ophthalmic Solution treatment group and placebo for the respective endpoint.

H_1 : There is a difference between the TOP1630 Ophthalmic Solution treatment group and placebo for the respective endpoint. A difference in favor of TOP1630 Ophthalmic Solutions will be considered a success for that endpoint.

All hypothesis testing will be two-sided with a type I error rate (α) of 0.10. There will be no adjustments for multiple endpoints or multiple treatment comparisons for this early phase, exploratory study. Specifics of the statistical tests are provided in Section 14.

4. Study Design and Procedures

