9.3 Definition of Baseline

Baseline measures are defined as the last measure prior to the initiation of study treatment, usually at Visit 2b. If a measure is taken both pre-CAE® and post-CAE®, the baseline will be the time point matched value at Visit 2b. For measures from daily subject diaries, baseline is defined as the average of all available days' readings during the run-in period, where daily scores are first obtained by averaging the AM and PM scores for that day, as applicable. For changes from pre-CAE® to post-CAE® post first treatment, the change from pre-CAE® to post-CAE® at Visit 2b will be considered the baseline value. For purposes of analysis, only subjects with at least 5 days of data in the run-in period will be included in change from baseline summaries and analyses.

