9.4 Data Analysis Conventions

All data analysis will be performed by SDC after the study is completed and the database has been locked and released for unmasking. Statistical programming and analyses will be performed using SAS® Version 9.4.

Quantitative variables will be summarized using descriptive statistics including the number of observations (n), mean, standard deviation (SD), median, minimum, and maximum values. Means, medians, and confidence intervals (CI) will be reported to two decimal places and SDs to three. Summaries for discrete variables will include frequency counts and percentages. All percentages will be rounded to one decimal place (i.e., XX.X%). Differences between the active treatment group and placebo will be calculated as Active minus Placebo and change from baseline will be calculated as follow-up visit minus baseline.

All efficacy analyses will be 2-sided at a significance level of 0.10. CIs for differences between treatment groups will be two-sided at 90% confidence. All p-values will be rounded to four decimal places; p-values less than 0.0001 will be presented as "<0.0001"; p-values greater than 0.9999 will be presented as ">0.9999".

All summaries will be presented by treatment group. Summaries of data from the Comfort Assessment and Safety and Efficacy Assessment of the study will be summarized separately. Summaries will be provided for demographics, baseline medical history, concurrent therapies, and subject disposition.

For the purpose of summarization, the following will be coded to the Medical Dictionary for Regulatory Activities (MedDRA) and World Health Organization (WHO) Drug Dictionary Enhanced (DDE), as appropriate: medical history, concurrent therapies, and AEs.

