16.12.2 ORA CALIBRA® OCULAR DISCOMFORT SCALE DURING CAE®

16.13 Ocular Protection Index (OPI) 2.0

Ocular protection index (OPI) will be assessed at Visits 2b and 4b, Pre-CAE®, on both eyes using the

The OPI and IBI will be summarized by visit using quantitative summary statistics. Change from baseline will also be summarized.

Statistical comparisons will employ two-sample *t*-tests as the primary method of analysis. An ANCOVA model adjusting for baseline will also be assessed as a sensitivity analysis.

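### Ten SAP efficacy sections make the two-sample t-test primary without saying whether it is read on visit score or on change; the baseline-adjusted ANCOVA already planned could lead at almost no cost

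*SAP*

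**What the plan says.** The sentence "Statistical comparisons will employ two-sample *t*-tests as the primary method of analysis" stands in the visible text of ten SAP sections: 16.4 to 16.11, 16.12.1 and 16.13. SAP section 16 sets the scale of analysis: "All visit-based data will be analyzed at each visit as well as change from baseline". It applies t-tests to both and, in the visible text, does not rank them.

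SAP 3.4 and Protocol 10.2 attach a conclusion to each endpoint: "A difference in favor of TOP1630 Ophthalmic Solutions will be considered a success for that endpoint". SAP 9.4 sets the threshold: "All efficacy analyses will be 2-sided at a significance level of 0.10".

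Baseline-adjusted ANCOVA is already in the plan:

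- Section 16 plans it for change from baseline in the listed measures, which include OSDI and ocular discomfort.
- Sections 16.4–16.8, 16.10 and 16.11 repeat it as an additional analysis.
- Section 16.2 says "An ANCOVA model will be used to compare the change from baseline for ocular discomfort".
- Section 16.13 gives it a lower rank: "An ANCOVA model adjusting for baseline will also be assessed as a sensitivity analysis".

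The covariate is also defined. For measures taken before and after CAE, SAP 9.3 says "the baseline will be the time point matched value at Visit 2b". For pre-to-post-CAE change, the same section uses the corresponding Visit 2b change. Protocol 10.4.7 lists t-test, Wilcoxon test and ANCOVA and calls none of them primary.

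**The concern.** Each variable, visit and time point can have two t-test results with equal claim to be primary, one on the score and one on the change. They can fall on opposite sides of 0.10, and the visible text does not say which one decides success.

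Fixing the choice in advance between the two t-tests would be a guess. Which is stronger depends on the correlation between baseline and follow-up and on the ratio of their SDs, and the documents give neither. With about 30 subjects per arm and a stated aim of informing the size of later trials, the loss of precision from a wrong guess can be substantial.

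ANCOVA avoids the choice. With baseline in the model, analysing the score or the change gives the same treatment estimate and p-value.

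**Working it through.** **The plan's own figure.** The documents give no efficacy power. Their one design figure is a 79% chance of seeing an adverse event with a true rate of 5%. This reproduces per arm: 1 − 0.95^30 = 0.785.

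**Inputs from the documents.** 30 per arm (SAP 4.1) and two-sided alpha 0.10 (SAP 9.4).

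**Assumed inputs.** The documents state no effect, correlation or SD.

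- Effect d of 0.3, 0.5 or 0.8 follow-up SD, and also 0.642, which gives about 80% power for the score t-test: (1.645 + 0.842) × √(2/30) = 0.642.
- Correlation r of 0, 0.3, 0.5 or 0.7.
- Baseline SD equal to k = 1.0, 0.8 or 0.7 times follow-up SD. Values below 1 allow for the Visit 2b entry limits in Protocol 5.2 (tear film break-up time, Schirmer, OSDI), which may narrow the baseline spread.
- No dropout.

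**Formulas.** With follow-up SD = 1, the variance V per subject is:

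- score t-test: 1 (58 df)
- change t-test: 1 + k² − 2rk (58 df)
- ANCOVA: (1 − r²)(1 + 1/56) (57 df), which does not depend on k

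Power comes from the noncentral t distribution with noncentrality d / √(V × 2/30). For d = 0.5 and V = 1 this is 0.5 / 0.258 = 1.94.

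The change t-test beats the score t-test only when k² < 2rk, that is r > k/2. The crossover is at r = 0.5, 0.4 and 0.35 for k = 1.0, 0.8 and 0.7.

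Two worked cases:

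- r = 0.5, k = 1.0: change V = 1 + 1 − 1 = 1; ANCOVA V = 0.75 × 1.018 = 0.763.
- r = 0.7, k = 0.7: change V = 1 + 0.49 − 0.98 = 0.51; ANCOVA V = 0.51 × 1.018 = 0.519. Here the change t-test is very slightly ahead.

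**Power at d = 0.5 (%)**

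| Method | r = 0 | r = 0.3 | r = 0.5 | r = 0.7 |
|---|---|---|---|---|
| Score t-test | 60.6 | 60.6 | 60.6 | 60.6 |
| Change t-test, k = 1.0 | 38.7 | 49.0 | 60.6 | 79.6 |
| Change t-test, k = 0.8 | 44.1 | 55.3 | 67.1 | 84.4 |
| Change t-test, k = 0.7 | 47.0 | 58.2 | 69.4 | 85.0 |
| ANCOVA, any k | 60.0 | 63.4 | 70.7 | 84.4 |

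**ANCOVA minus the better t-test, d = 0.5 (points)**

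| k | r = 0 | r = 0.3 | r = 0.5 | r = 0.7 |
|---|---|---|---|---|
| 1.0 | −0.7 | +2.8 | +10.1 | +4.8 |
| 0.8 | −0.7 | +2.8 | +3.6 | 0.0 |
| 0.7 | −0.7 | +2.8 | +1.3 | −0.6 |

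Against the worse t-test, ANCOVA gains from 5 points (r = 0.3, k = 0.7) to 24 points (r = 0.7).

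**Other effects.** Gain over the better t-test for r = 0.3 / 0.5 / 0.7, over k from 0.7 to 1.0:

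- d = 0.3: 1.6 / 0.8 to 6.0 / −0.6 to 4.4 points
- d = 0.8: 1.6 / 0.4 to 4.7 / 0.0 to 0.6 points

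**How often the two t-tests disagree on p<0.10.** Simulation with 40,000 trials per setting, r 0.3–0.7, k 0.7–1.0:

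| Effect (SD) | Disagreement |
|---|---|
| 0 | 11–16% |
| 0.3 | 20–37% |
| 0.5 | 22–35% |
| 0.642 | 16–26% |
| 0.8 | 7–16% |

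**With no effect.** At least one of the two t-tests falls below 0.10 in 15–18% of trials, against 10% for the single ANCOVA. Counting only results in favour of TOP1630, this is 7–9% against 5%. Simulated ANCOVA rejection under no effect was 9.9–10.4%.

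**Identity.** ANCOVA fitted to the score and to the change gave the same treatment estimate and p-value up to rounding error.

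**The case against.** The strongest reply is that little depends on the label. The testing is declared exploratory, the trial is not powered for efficacy, and multiplicity is openly unadjusted. ANCOVA will be run anyway, so those planning later trials will have its estimates whichever method is called primary. That stands and is why the point is minor. It does not settle which result counts within one endpoint once the plan ties a success statement to it.

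The reach is limited. The plan's key endpoints are corneal staining and ocular discomfort. Of the ten sections, only 16.12.1 concerns one of these, and the visible part of 16.2 already describes ANCOVA for change. This also stands.

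Parts of section 16 are not visible. The bold type that marks topline tables and figures did not survive extraction, and some figure titles in SAP section 23 do show a choice of scale. The finding is therefore confined to visible text, and nothing is claimed about 16.1, 16.3 or 16.12.2 or about ANCOVA being absent from 16.9 or 16.12.1. A figure title also does not name the leading test.

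The sizes rest on assumed inputs and a continuous model, while some of the scales are ordinal. The gain of 10.1 points over the better t-test needs r = 0.5 and equal SDs. If entry limits narrow the baseline (k of 0.7 to 0.8), the range is −0.7 to +3.6 points. This is accepted. The case rests on ANCOVA staying close to or above the better t-test without knowing which that is.

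**Conclusion.** The concern holds, as a minor matter of efficiency and clarity. The t-tests are valid, so this is not an error. At 30 per arm, two-sided 0.10 and an assumed 0.5 SD effect, letting ANCOVA lead changes power by −0.7 to +10.1 points against the better t-test and by +5 to +24 points against the worse one. It also replaces two results that disagree in 22–35% of such trials (r 0.3–0.7) with one. These figures depend on assumed correlations (0–0.7), SD ratios (0.7–1.0) and effects. The direction of the advice does not depend on knowing them, since the largest loss found was under 1 point. It gives one lead result per variable, visit and time point, but does not rank those against each other.

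**What to change.** In SAP section 16 and in 16.4–16.11, 16.12.1 and 16.13, name ANCOVA with treatment and the time-point-matched Visit 2b baseline as the primary method for each visit-based efficacy variable. Include OSDI (16.9) and pre- and post-CAE ocular discomfort (16.2 and 16.12.1). For pre-to-post-CAE change, the covariate is the Visit 2b pre-to-post change that SAP 9.3 already defines. State that success under SAP 3.4 is read from this model, and keep the t-test and Wilcoxon test as supportive.

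The cost is SAP wording only. No new data, visits or models are needed, and Protocol 10.4.7 is not contradicted because it names no primary method. The downsides are up to about 0.7 point of power if baseline is unrelated to outcome, about 0.6 point against the change t-test at r = 0.7 and k = 0.7, and an assumed linear relation with baseline, to be checked with residual plots.
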